## 11. MEASUREMENT OF EFFECT

### 11.1 Antitumor Effect – Solid Tumors

For the purposes of this study, participants should be re-evaluated for response every 8 weeks (or as clinically indicated). In addition to a baseline scan, confirmatory scans should also be obtained 8 weeks following initial documentation of objective response.

CONFIDENTIAL

*This document is confidential. Do not disclose or use except as authorized.*

IRB APPROVED

Response and progression will be evaluated in this study using the new international criteria proposed by the Response Evaluation Criteria in Solid Tumors (RECIST) guideline (version 1.1) [Eur J Ca 45:228-247, 2009]. Changes in the largest diameter (unidimensional measurement) of the tumor lesions and the shortest diameter in the case of malignant lymph nodes are used in the RECIST criteria.

#### 11.1.1 Definitions

Evaluable for Target Disease response. Only those participants who have measurable disease present at baseline, have received at least one cycle of therapy, and have had their disease re-evaluated will be considered evaluable for target disease response. These participants will have their response classified according to the definitions stated below. (Note: Participants who exhibit objective disease progression prior to the end of cycle 1 will also be considered evaluable.)

Evaluable Non-Target Disease Response. Participants who have lesions present at baseline that are evaluable but do not meet the definitions of measurable disease, have received at least one cycle of therapy, and have had their disease re-evaluated will be considered evaluable for non-target disease. The response assessment is based on the presence, absence, or unequivocal progression of the lesions.

#### 11.1.2 Disease Parameters

Measurable disease. Measurable lesions are defined as those that can be accurately measured in at least one dimension (longest diameter to be recorded) as  $\geq 20$  mm by chest x-ray or  $\geq 10$  mm with CT scan, MRI, or calipers by clinical exam. All tumor measurements must be recorded in millimeters (or decimal fractions of centimeters).

Note: Tumor lesions that are situated in a previously irradiated area might or might not be considered measurable.

Malignant lymph nodes. To be considered pathologically enlarged and measurable, a lymph node must be  $\geq 15$  mm in short axis when assessed by CT scan (CT scan slice thickness recommended to be no greater than 5 mm). At baseline and in follow-up, only the short axis will be measured and followed.

Non-measurable disease. All other lesions (or sites of disease), including small lesions (longest diameter  $<10$  mm or pathological lymph nodes with  $\geq 10$  to  $<15$  mm short axis), are considered non-measurable disease. Bone lesions, leptomeningeal disease, ascites, pleural/pericardial effusions, lymphangitis cutis/pulmonitis, inflammatory breast disease, abdominal masses (not followed by CT or MRI), and cystic lesions are all considered non-measurable.

Note: Cystic lesions that meet the criteria for radiographically defined simple cysts should not be considered as malignant lesions (neither measurable nor non-measurable)

---

CONFIDENTIAL

*This document is confidential. Do not disclose or use except as authorized.*

IRB APPROVED

since they are, by definition, simple cysts.

‘Cystic lesions’ thought to represent cystic metastases can be considered as measurable lesions, if they meet the definition of measurability described above. However, if non-cystic lesions are present in the same participant, these are preferred for selection as target lesions.

**Target lesions.** All measurable lesions up to a maximum of 2 lesions per organ and 5 lesions in total, representative of all involved organs, should be identified as **target lesions** and recorded and measured at baseline. Target lesions should be selected on the basis of their size (lesions with the longest diameter), be representative of all involved organs, but in addition should be those that lend themselves to reproducible repeated measurements. It may be the case that, on occasion, the largest lesion does not lend itself to reproducible measurement in which circumstance the next largest lesion which can be measured reproducibly should be selected. A sum of the diameters (longest for non-nodal lesions, short axis for nodal lesions) for all target lesions will be calculated and reported as the baseline sum diameters. If lymph nodes are to be included in the sum, then only the short axis is added into the sum. The baseline sum diameters will be used as reference to further characterize any objective tumor regression in the measurable dimension of the disease.

**Non-target lesions.** All other lesions (or sites of disease) including any measurable lesions over and above the 5 target lesions should be identified as **non-target lesions** and should also be recorded at baseline. Measurements of these lesions are not required, but the presence, absence, or in rare cases unequivocal progression of each should be noted throughout follow up.

#### 11.1.3 Methods for Evaluation of Disease

All measurements should be taken and recorded in metric notation using a ruler, calipers, or a digital measurement tool. All baseline evaluations should be performed as closely as possible to the beginning of treatment and never more than 4 weeks before the beginning of the treatment.

The same method of assessment and the same technique should be used to characterize each identified and reported lesion at baseline and during follow-up. Imaging-based evaluation is preferred to evaluation by clinical examination unless the lesion(s) being followed cannot be imaged but are assessable by clinical exam.

**Clinical lesions.** Clinical lesions will only be considered measurable when they are superficial (e.g., skin nodules and palpable lymph nodes) and  $\geq 10$  mm in diameter as assessed using calipers (e.g., skin nodules). In the case of skin lesions, documentation by color photography, including a ruler to estimate the size of the lesion, is recommended.

**Chest x-ray.** Lesions on chest x-ray are acceptable as measurable lesions when they are clearly defined and surrounded by aerated lung; however, CT is preferable.

---

CONFIDENTIAL

*This document is confidential. Do not disclose or use except as authorized.*

IRB APPROVED

Conventional CT and MRI. This guideline has defined measurability of lesions on CT scan based on the assumption that CT thickness is 5mm or less. If CT scans have slice thickness greater than 5 mm, the minimum size of a measurable lesion should be twice the slice thickness. MRI is also acceptable in certain situations (e.g. for body scans).

Use of MRI remains a complex issue. MRI has excellent contrast, spatial, and temporal resolution; however, there are many image acquisition variables involved in MRI, which greatly impact image quality, lesion conspicuity, and measurement. Furthermore, the availability of MRI is variable globally. As with CT, if an MRI is performed, the technical specifications of the scanning sequences used should be optimized for the evaluation of the type and site of disease. Furthermore, as with CT, the modality used at follow-up should be the same as was used at baseline and the lesions should be measured/assessed on the same pulse sequence. It is beyond the scope of the RECIST guidelines to prescribe specific MRI pulse sequence parameters for all scanners, body parts, and diseases. Ideally, the same type of scanner should be used and the image acquisition protocol should be followed as closely as possible to prior scans. Body scans should be performed with breath-hold scanning techniques, if possible.

FDG-PET. While FDG-PET response assessments need additional study, it is sometimes reasonable to incorporate the use of FDG-PET scanning to complement CT scanning in assessment of progression (particularly possible 'new' disease). New lesions on the basis of FDG-PET imaging can be identified according to the following algorithm:

- (a) Negative FDG-PET at baseline, with a positive FDG-PET at follow-up is a sign of PD based on a new lesion.
- (b) No FDG-PET at baseline and a positive FDG-PET at follow-up: If the positive FDG-PET at follow-up corresponds to a new site of disease confirmed by CT, this is PD. If the positive FDG-PET at follow-up is not confirmed as a new site of disease on CT, additional follow-up CT scans are needed to determine if there is truly progression occurring at that site (if so, the date of PD will be the date of the initial abnormal FDG-PET scan). If the positive FDG-PET at follow-up corresponds to a pre-existing site of disease on CT that is not progressing on the basis of the anatomic images, this is not PD.
- (c) FDG-PET may be used to upgrade a response to a CR in a manner similar to a biopsy in cases where a residual radiographic abnormality is thought to represent fibrosis or scarring. The use of FDG-PET in this circumstance should be prospectively described in the protocol and supported by disease-specific medical literature for the indication. However, it must be acknowledged that both approaches may lead to false positive CR due to limitations of FDG-PET and biopsy resolution/sensitivity.

Note: A 'positive' FDG-PET scan lesion means one which is FDG avid with an uptake greater than twice that of the surrounding tissue on the attenuation corrected image.

PET-CT. At present, the low dose or attenuation correction CT portion of a combined PET-CT is not always of optimal diagnostic CT quality for use with RECIST

measurements. However, if the site can document that the CT performed as part of a PET-CT is of identical diagnostic quality to a diagnostic CT (with IV and oral contrast), then the CT portion of the PET-CT can be used for RECIST measurements and can be used interchangeably with conventional CT in accurately measuring cancer lesions over time. Note, however, that the PET portion of the CT introduces additional data which may bias an investigator if it is not routinely or serially performed.

MIBG (meta-iodobenzylguanidine). The following is recommended, to assure high quality images are obtained.

Patient preparation: Iodides, usually SSKI (saturated solution of potassium iodide), are administered to reduce thyroidal accumulation of free radioiodine, preferably beginning the day prior to injection and continuing for 3 additional days (4 days total). For infants and children, one drop t.i.d. is sufficient, for adolescents 2 drops t.i.d., and for adults 3 drops t.i.d. Participants and/or parents are asked about exposure to potential interfering agents. If none is noted, an indwelling intravenous line is established. The dose of MIBG is administered by slow intravenous injection over 90 seconds. Images from the head to the distal lower extremities should be obtained.

I-123MIBG scintigraphy is performed to obtain both planar and tomographic images. Planar: Anterior and posterior views from the top of the head to the proximal lower extremities are obtained for 10 minutes at 24 hours and occasionally at 48 hours following injection of 10 mCi/1.7 square meters of body surface area ( $\sim 150 \mu\text{Ci/kg}$ , maximum 10 mCi). Anterior views of the distal lower extremities are adequate. A large field of view dual head gamma camera with low energy collimators is preferred.

SPECT: Most participants receiving I-123 MIBG also undergo SPECT at 24 hours, using a single or multi-headed camera with a low energy collimator. The camera is rotated through 360 degrees, 120 projections at 25 seconds per stop. Data are reconstructed using filtered back projections with a Butterworth filter and a cut off frequency of 0.2-0.5. SPECT/CT may be performed at institutions with this capacity.

Ultrasound. Ultrasound is not useful in assessment of lesion size and should not be used as a method of measurement. Ultrasound examinations cannot be reproduced in their entirety for independent review at a later date and, because they are operator dependent, it cannot be guaranteed that the same technique and measurements will be taken from one assessment to the next. If new lesions are identified by ultrasound in the course of the study, confirmation by CT or MRI is advised. If there is concern about radiation exposure from CT, MRI may be used instead of CT in selected instances.

Endoscopy, Laparoscopy. The utilization of these techniques for objective tumor evaluation is not advised. However, such techniques may be useful to confirm complete pathological response when biopsies are obtained or to determine relapse in trials where recurrence following complete response (CR) or surgical resection is an endpoint.

Tumor markers. Tumor markers alone cannot be used to assess response. If markers are

initially above the upper normal limit, they must normalize for a participant to be considered in complete clinical response. Specific guidelines for both CA-125 response (in recurrent ovarian cancer) and PSA response (in recurrent prostate cancer) have been published [JNCI 96:487-488, 2004; J Clin Oncol 17, 3461-3467, 1999; J Clin Oncol 26:1148-1159, 2008]. In addition, the Gynecologic Cancer Intergroup has developed CA-125 progression criteria which are to be integrated with objective tumor assessment for use in first-line trials in ovarian cancer [JNCI 92:1534-1535, 2000].

Cytology, Histology. These techniques can be used to differentiate between partial responses (PR) and complete responses (CR) in rare cases (e.g., residual lesions in tumor types, such as germ cell tumors, where known residual benign tumors can remain).

The cytological confirmation of the neoplastic origin of any effusion that appears or worsens during treatment when the measurable tumor has met criteria for response or stable disease is mandatory to differentiate between response or stable disease (an effusion may be a side effect of the treatment) and progressive disease.

#### 11.1.4 Response Criteria

##### 11.1.4.1 Evaluation of Target Lesions

Complete Response (CR): Disappearance of all target lesions. Any pathological lymph nodes (whether target or non-target) must have reduction in short axis to <10 mm.

Partial Response (PR): At least a 30% decrease in the sum of the diameters of target lesions, taking as reference the baseline sum diameters.

Progressive Disease (PD): At least a 20% increase in the sum of the diameters of target lesions, taking as reference the smallest sum on study (this includes the baseline sum if that is the smallest on study). In addition to the relative increase of 20%, the sum must also demonstrate an absolute increase of at least 5 mm. (Note: the appearance of one or more new lesions is also considered progressions).

Stable Disease (SD): Neither sufficient shrinkage to qualify for PR nor sufficient increase to qualify for PD, taking as reference the smallest sum diameters while on study.

##### 11.1.4.2 Evaluation of Non-Target Lesions

Complete Response (CR): Disappearance of all non-target lesions and normalization of tumor marker level. All lymph nodes must be non-pathological in size (<10 mm short axis).

Note: If tumor markers are initially above the upper normal limit, they must normalize for a patient to be considered in complete clinical response.

---

CONFIDENTIAL

*This document is confidential. Do not disclose or use except as authorized.*

IRB APPROVED

**Non-CR/Non-PD:** Persistence of one or more non-target lesion(s) and/or maintenance of tumor marker level above the normal limits.

**Progressive Disease (PD):** Appearance of one or more new lesions and/or unequivocal progression of existing non-target lesions. Unequivocal progression should not normally trump target lesion status. It must be representative of overall disease status change, not a single lesion increase.

Although a clear progression of “non-target” lesions only is exceptional, the opinion of the treating physician should prevail in such circumstances, and the progression status should be confirmed at a later time by the review panel (or Principal Investigator).

#### 11.1.4.3 Evaluation of New Lesions

The finding of a new lesion should be unequivocal (i.e. not due to difference in scanning technique, imaging modality, or findings thought to represent something other than tumor (for example, some ‘new’ bone lesions may be simply healing or flare of pre-existing lesions). However, a lesion identified on a follow-up scan in an anatomical location that was not scanned at baseline is considered new and will indicate PD. If a new lesion is equivocal (because of small size etc.), follow-up evaluation will clarify if it truly represents new disease and if PD is confirmed, progression should be declared using the date of the initial scan on which the lesion was discovered.

#### 11.1.4.4 Evaluation of Best Overall Response

The best overall response is the best response recorded from the start of the treatment until disease progression/recurrence (taking as reference for progressive disease the smallest measurements recorded since the treatment started). The patient's best response assignment will depend on the achievement of both measurement and confirmation criteria.

#### For Participants with Measurable Disease (i.e., Target Disease)

Target Lesions	Non-Target Lesions	New Lesions	Overall Response	Best Overall Response when Confirmation is Required*
CR	CR	No	CR	≥4 wks Confirmation**
CR	Non-CR/Non-PD	No	PR	≥4 wks Confirmation**
CR	Not evaluated	No	PR	
PR	Non-CR/Non-PD/not evaluated	No	PR	
SD	Non-CR/Non-	No	SD	Documented at least once ≥4

---

CONFIDENTIAL

This document is confidential. Do not disclose or use except as authorized.

IRB APPROVED

	PD/not evaluated			wks from baseline**	
PD	Any	Yes or No	PD	no prior SD, PR or CR	
Any	PD***	Yes or No	PD		
Any	Any	Yes	PD		

* See RECIST 1.1 manuscript for further details on what is evidence of a new lesion.
 
** Only for non-randomized trials with response as primary endpoint.
 
*** In exceptional circumstances, unequivocal progression in non-target lesions may be accepted as disease progression.
					

Note: Participants with a global deterioration of health status requiring discontinuation of treatment without objective evidence of disease progression at that time should be reported as “symptomatic deterioration.” Every effort should be made to document the objective progression even after discontinuation of treatment.
					

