**IRB APPROVED**

described below may be administered with the intent to treat the participant's malignancy during the course of treatment.

The treatment plan is shown below:

Nivolumab infusion at a dose of 3mg/kg, once every 2 weeks, until treatment discontinuation.  
Ipilimumab infusion at a dose of 1mg/kg, once every 6 weeks, until treatment discontinuation.

For DTC and MTC patients, there will be randomization to 2 arms for a lead-in phase in this study:

- Arm 1: Nivolumab starts 2 weeks prior to Ipilimumab
- Arm 2: Ipilimumab starts 2 weeks prior to Nivolumab

The following stratification factor will be used in order to prevent imbalance across treatment arms:

- Histology (differentiated thyroid cancer vs. medullary thyroid cancer)

**Infusion schedule Arm 1:** Same schedule will be followed beyond week 17 until 24 months from first study treatment, or until treatment discontinuation.

	Wk1	Wk3	Wk5	Wk7	Wk9	Wk11	Wk13	Wk15	Wk17
Nivolumab	X	X	X	X	X	X	X	X	X
Ipilimumab		X			X			X	

**Infusion schedule Arm 2:** Same schedule will be followed beyond week 17 until 24 months from first study treatment, or until treatment discontinuation.

	Wk1	Wk3	Wk5	Wk7	Wk9	Wk11	Wk13	Wk15	Wk17
Ipilimumab	X			X			X		
Nivolumab		X	X	X	X	X	X	X	X

No difference in efficacy between the 2 arms is expected and endpoint analysis will be performed based on both arms combined.

Due to the aggressive nature of their disease, for patients with anaplastic thyroid cancer, both drugs will start synchronously on day 1. No randomization or lead-in phase will occur for these patients.

**Infusion schedule Arm 3:** Same schedule will be followed beyond week 17 until 24 months from first study treatment, or until treatment discontinuation.

	Wk1	Wk3	Wk5	Wk7	Wk9	Wk11	Wk13	Wk15	Wk17
Ipilimumab	X			X			X		
Nivolumab	X	X	X	X	X	X	X	X	X

This design will allow us to obtain liquid and in some cases tumor tissue biopsies sequentially that will provide valuable information about biological endpoints including changes in T cell invasion, release of inflammatory cytokines, cell death and RNA expression profile, cell free DNA, and circulating tumor cells at baseline, while on one drug alone, on both drugs and at the time of progression.

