### **13. STATISTICAL CONSIDERATIONS**

Prior to Amendment 7, patients with DTC, MTC, and ATC were randomized to Arms 1 and 2. With approval of Amendment 7, patients with ATC were no longer randomized into Arms 1 and 2, but rather registered into Arm 3 (for a total of n=7 patients with ATC entered into Arms 1, 2, and 3). With approval of Amendment 12, the accrual for the ATC cohort was increased to n=10.

The primary objective of this trial is to evaluate efficacy in terms of best overall response rate (CR+PR) for patients with DTC. The purpose of the randomization with nivolumab and ipilimumab starting sequentially is to provide opportunities via the correlatives to study the specific immunologic changes that occur in response to either drug alone as well as both drugs in combination. Although patients will be randomized between arms, no differences in terms of efficacy are expected, therefore, for the primary endpoint of response, the arms will be analyzed together.

A two -stage design (Simon's minimax design) will be used to minimize the number of pts enrolled. Twenty-three eligible patients with differentiated thyroid cancer (DTC) who start protocol treatment are to be accrued in the first stage. If there are  $\leq$  2 patients with DTC with

---

*CONFIDENTIAL*

*This document is confidential. Do not disclose or use except as authorized.*

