**IRB APPROVED**

disease in response, accrual to this trial will be closed with the expectation that there is little evidence that the response rate will reach 25%. The probability that the trial will close early is 59% if the true response rate is 10%. If there are >2 patients with DTC with disease in response, accrual will continue until a total of 32 eligible patients with DTC who start protocol treatment are entered. If there are >5 patients with DTC with disease in response among 32 eligible patients with DTC who began protocol treatment, further testing of this regimen will be considered. If the true response rate is 25%, the probability of concluding the regimen is effective is 84%, if the true response rate is 10%, the probability of concluding the regimen is effective is 9%. In addition, n=7 medullary and n=10 anaplastic thyroid patients will also be included as exploratory cohorts. Allowing for patients to be declared ineligible and/or not start protocol treatment after registration, a total of 54 pts will be entered into Arms 1, 2, and 3. The following stratification factor will be used for Arms 1 and 2 only in order to prevent imbalance across treatment arms:

- Histology (differentiated thyroid cancer vs. medullary thyroid cancer)

(Prior to Amendment 7, patients with anaplastic thyroid cancer were also randomized, and as of approval of Amendment 7, patients with anaplastic thyroid cancer will no longer be randomized, they will instead be entered into Arm 3 (see schema and section 5 for details)).

The primary efficacy population includes all eligible patients with DTC who begin protocol treatment. Best overall response will be summarized as a proportion with a corresponding exact 95% confidence interval (CI) (if the trial closes to accrual after the first stage), or a corresponding 95% two-stage CI if the trial closes to accrual after the second stage. Best overall response for patients with medullary and anaplastic thyroid cancer will also be summarized.

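### A footnote in Section 11.1.4.4 exempts the randomized DTC cohort from response confirmation, contradicting that section's own definition of the primary endpoint

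*Combined protocol and SAP*

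**What the plan says.** Section 13 sets the endpoint: "The primary objective of this trial is to evaluate efficacy in terms of best overall response rate (CR+PR) for patients with DTC". Section 11.1.4.4 defines that term: "The patient's best response assignment will depend on the achievement of both measurement and confirmation criteria". Section 11.1 adds that "confirmatory scans should also be obtained 8 weeks following initial documentation of objective response".

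The table for participants with measurable disease, also in Section 11.1.4.4, asks for confirmation at 4 weeks or later. A double-asterisk footnote restricts that requirement: "Only for non-randomized trials with response as primary endpoint". The stable-disease row carries the same mark.

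Section 5.1 states: "For DTC and MTC patients, there will be randomization to 2 arms for a lead-in phase in this study". Section 13 adds that "for the primary endpoint of response, the arms will be analyzed together", and tests the pooled group against a fixed 10% response rate.

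The final decision rule in Section 13 begins: "If there are >5 patients with DTC with disease in response among 32 eligible patients with DTC who began protocol treatment". The stage 1 rule (more than 2 of 23) is worded in the same way. The reported estimate is described thus: "Best overall response will be summarized as a proportion with a corresponding exact 95% confidence interval" if accrual stops after stage 1, with a two-stage interval otherwise. None of these sentences says whether a response must be confirmed.

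**The concern.** The DTC cohort is randomized, so the footnote's literal wording takes it out of the confirmation requirement. The defining sentence of the same section puts it in. Section 13 uses the term best overall response, which sends the reader back to Section 11.1.4.4 and so to the contradiction.

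Two analysts could each follow a written rule and count different numbers of responders from the same scans. The margins are small. At exactly 3 of 23 or 6 of 32, removing one unconfirmed responder turns continue into stop, or positive into negative. The definition should be fixed before anyone counts.

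The 4-week minimum and the 8-week confirmatory scan are compatible and are not at issue, since a scan at 8 weeks satisfies a minimum of 4.

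**Working it through.** **Inputs from Section 13.** Stage 1: n1 = 23, stop if 2 or fewer responses. Final: n = 32 (9 more patients), positive if more than 5. Null rate 10%, target rate 25%.

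**Formulas.** With per-patient response probability p:

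- Early stopping: PET(p) = P(X1 ≤ 2), X1 ~ Bin(23, p).
- Positive trial: Pos(p) = Σ over x = 3 to 23 of P(X1 = x) · P(X2 ≥ 6 − x), X2 ~ Bin(9, p).

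**The plan's own figures.** PET(0.10) = 0.0886 + 0.2265 + 0.2768 = 0.592 (stated 59%). Pos(0.10) = 0.0919 (stated 9%). Pos(0.25) = 0.840 (stated 84%). All three reproduce, so the design arithmetic is sound.

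**How often the readings disagree.** Let u be the share of responders who fail confirmation, independently between patients. The documents do not give u; 5%, 10%, 20% and 30% are assumed. If the any-response rate is p, the confirmed rate is p(1 − u). On the same data the confirmed count never exceeds the any-response count at either stage. A trial positive on confirmed responses is therefore also positive on all responses, and the probabilities subtract exactly:

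- Opposite final conclusion = Pos(p) − Pos(p(1 − u)).
- Opposite stage 1 decision = PET(p(1 − u)) − PET(p).

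Example, p = 0.25 and u = 0.10: the confirmed rate is 0.225. Final: 0.8402 − 0.7498 = 0.090. Stage 1: 0.0825 − 0.0492 = 0.033.

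| u | Final, p = 25% | Stage 1, p = 25% | Final, p = 10% | Stage 1, p = 10% |
|---|---|---|---|---|
| 5% | 4.2% | 1.5% | 1.6% | 3.2% |
| 10% | 9.0% | 3.3% | 3.1% | 6.5% |
| 20% | 20.9% | 8.4% | 5.4% | 13.0% |
| 30% | 35.1% | 15.8% | 7.1% | 19.3% |

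These figures need no assumption about the definition behind the 10% and 25% rates.

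**Error rates, only if definitions are mismatched.** The documents do not show a mismatch. The two possibilities are:

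- The 10% is a confirmed rate but unconfirmed responses are counted. The counted rate is 0.10/(1 − u), and type I error is Pos(0.10/(1 − u)).
- The 25% includes unconfirmed responses but only confirmed ones are counted. The counted rate is 0.25(1 − u), and power is Pos(0.25(1 − u)).

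| u | Type I error (9.2% if matched) | Power (84.0% if matched) |
|---|---|---|
| 5% | 11.1% | 79.9% |
| 10% | 13.4% | 75.0% |
| 20% | 19.9% | 63.1% |
| 30% | 29.7% | 49.0% |

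**The case against.** The strongest reply is that the intent can be recovered. The endpoint is named best overall response, Section 11.1.4.4 makes that depend on confirmation, and Section 11.1 calls for confirmatory scans in this study specifically. Randomization serves the correlative work only. Response is pooled and tested against a fixed rate, which is the single-group setting the footnote seems to have in mind. The footnote also looks like template text: Section 11 carries material on CA-125, PSA and imaging of infants as well. The last paragraph of Section 13 mentions confirmation of response status when discussing the accrual pause. Finally, the size of the effect rests on an assumed failure share, and no printed figure is wrong.

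Much of this stands. Confirmation is the likelier intent, the operating characteristics are right, and the percentages show how far two readings diverge, not how likely a wrong decision is. But template text left in a protocol is still operative. Asking for a confirmatory scan does not say that an unconfirmed response is left out of the count. The accrual-pause sentence may mean only that response status has been ascertained, and it does not govern the decision rules. Nothing in the plan overrides the footnote or ties those rules to confirmed responses.

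**Conclusion.** The contradiction is real and should be fixed. The primary endpoint has two countings that the text supports, and the footnote followed literally admits unconfirmed responders to both decisions. With an assumed 5% to 30% of responders failing confirmation, independently between patients, the final conclusion differs between readings in 4.2% to 35.1% of trials at a true any-response rate of 25%. At 10%, the stage 1 decision differs in 3.2% to 19.3%. The upper ends depend on the 30% assumption, which the documents neither support nor exclude. Type I error and power move only if counts and design rates use different definitions.

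**What to change.** - Reword the footnote for the CR and PR rows so that it does not exempt the pooled DTC cohort. Treat the stable-disease row as a separate, deliberate choice.
- State in Section 13 that both decision rules count CR or PR confirmed at least 4 weeks later under Section 11.1.4.4, and report unconfirmed responses separately.
- Have the sponsor state whether 10% and 25% are confirmed rates, and restate the operating characteristics if they are not.

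If the sponsor in fact meant to count unconfirmed responses, saying so and amending the definition in Section 11.1.4.4 would also remove the ambiguity.

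The change is to wording only. Counting confirmed responses lowers the observed rate slightly, and if the 25% was meant to include unconfirmed responses, power falls as tabulated above. The stage 1 decision may have to wait for pending confirmations, usually up to 8 weeks. The wait can be longer for patients off treatment (assessed every 3 months, give or take 1 month, per the Section 10 calendar notes) or on a treatment hold (Section 6.9, where the investigator sets scan timing).
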